Study participants will be assigned into one of two study arms, intervention or control, based on random assignment to the two designated units. At the time of consent, patients will be informed that there are two study arms and that some subjects will receive enhanced pain management education; however, subjects will not explicitly be informed if they are in the intervention or control arm of the study. Participants who have verbally consented will receive a HIPAA authorization form accompanied by a letter reminding them of the study and their consent to participate at the time of the preoperative visit. This typically occurs one to two days before surgery. Participants will be asked to sign the HIPAA authorization form and return the clinical staff. Participants will be provided an extra copy for their records. No Patient data will be collected prior to this. Once HIPAA has been signed participants will complete the intake survey provided with the packet of information.

Researchers are blinded to the study arm the participant was enrolled in until after consent has been obtained, the patient is enrolled in the study, and has been admitted to the hospital and assigned a bed. Once enrolled and consented, bed control will be notified to assign the patient(s) to one of the two designated patient care units with no specific direction offered on which unit the patient(s) should be assigned to. The only direction provided will be to split the patients evenly between the two units. Only ten study arm participants may be enrolled and active at one time. This is limited based on the number of available iPad devices for the purposes of this study.

Study Population

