Enrollment into the study is completely voluntary. Participating in this study poses minimal risk to the participants; all patients will receive the necessary education to meet their care needs and the minimum standard of practice. The potential for risk is that the mode of information/education delivery does not meet the patients' needs and the risk of low acceptance of technology use. In this case, patients in the study arm would be removed from the study and would receive standard education. Pain management in both arms will remain the same; no changes will be made to the process for treating pain using either non-pharmacologic or pharmacologic interventions. Medication orders, medication administration, and pain treatment plans will not be affected by participation in study. As care is today, pain management will be customized to meet the needs of the individual patient.

Oral consent will be obtained, documented, and maintained as part of the research records. No identifiable patient information will be maintained. The only identifiable information collected will be the patients' clinic number. It will be used for tracking purposes only until the data collection process is complete. When the chart audit is complete, the clinic numbers will be removed from the data set and only the predesignated subject number will be used and maintained. At the start of the study the patient will be asked to complete the HIPAA Authorization to Use and Disclose Protected Health Information. The researcher will remain blinded to the type of education delivery that the patient will receive until after enrolment and bed assignment. This will prevent potential bias with inadvertently assigning patients to groups based on characteristics, like age.

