Pain knowledge. The Patient Pain Questionnaire (PPQ) will be used to evaluate pain knowledge post intervention (Appendix F). The PPQ is a 16-item questionnaire measuring both pain knowledge and actual experiences with pain. This study will use only nine of the items targeted at pain knowledge and beliefs. The nine knowledge-based questions use a ten-point (0-10) ordinal scale to assess patients' agreement or disagreement with statements about pain relief, medication administration, addiction, dosing, timing, non-pharmacologic management, side effects, beliefs about pain medications, and changes in the pain experience. Depending on the statement a higher score may indicate either agreement or disagreement with the statement. All items have been formatted so that zero indicates the most positive outcome and a ten indicates the most negative outcome. These nine items are primarily used for chronic cancer pain; however the PPQ has been and can be adapted to assess general pain knowledge and experiences. Psychometric analysis of the PPQ demonstrated content validity of 0.90 (content validity index), construct validity of <0.05 variance, concurrent validity ($r=0.60$; $p <0.05$), test-retest reliability ($r=0.80$), and internal consistency with a Cronbach α of 0.71 (Ferrel & Rivera, 1997). The language will also be revised, as in the study conducted by Reynolds (2009) and reference to chronic cancer pain will be removed from the original question. This tool is open source and available for application without further permission and may be utilized by clinicians or researchers (City of Hope Pain and Palliative Care Resource Center, 2017; MIDSS, n.d.).

At the start of the study and at the time of discharge the patient will complete the APS-POQ-R and the revised knowledge-based PPQ surveys. It will take participants approximately 10 minutes to complete the two surveys. The use of these two widely used instruments will ensure that the information being collected is highly reliable and valid, truly measuring what the study is seeking to evaluate. These paper and pencil surveys will be provided to the patient prior to discharge and collected from the patient by the staff registered nurse (RN) and/or charge nurse. In addition to training and education on the intervention, staff will receive direction on the data (survey) collection process and requirements.

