Data will be collected at three points in time using paper and pencil survey's and chart audits. The data collection protocol can be found in Appendix G. After completion of the HIPAA form, demographic and past medical history information and pain knowledge survey will be administered in the ambulatory clinic at the time of the perioperative surgical visit. A paper and pencil survey/form will be provided to the patient when they arrive in the clinic for their perioperative appointment and returned to the desk staff when completed.

The intervention will occur on the postoperative inpatient care unit (PCU) starting at the time the patient arrives on the unit from the post anesthesia care unit (PACU). The intervention will continue through the course of care until discharge. At the time of discharge the patient will complete the Revised American Pain Society Patient Outcomes Questionnaire (APS-POQ-R) (Gordon et al., 2010) and the revised knowledge-based Patient Pain Questionnaire (PPQ) (Ferrell & Rivera, 1997; Reynolds, 2009). The use of these two widely used instruments will ensure that the information being collected is highly reliable and valid, truly measuring what the study is seeking to evaluate. These paper and pencil survey's will be provided to the patient prior to discharge and collected from the patient by the staff registered nurse (RN) and/or charge nurse. In addition to training and education on the intervention, staff will receive direction on the data (survey) collection process and requirements. The administration of the post-intervention surveys at the point of care, before the patient has left the study environment, will help to prevent the loss of study participants due to non-response or failure to complete follow-up surveys.

After discharge the researcher will conduct a chart review to collect clinical data including opioid consumption totals, past medical history, anesthesia type, and length of stay. The researcher in addition to one RN will be responsible for chart audit data collection. The RNs will be trained by the researcher on chart audit processes. The RNs will complete the institutions IRB education requirements for staff assisting with research data. A tentative timeline has been developed as a GNATT chart in Appendix H. All collected data from the paper surveys' and chart audits will be entered in to SPSS for analysis. Data storage and management is discussed further under ethical considerations.

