Account, member, certificate or professional license numbers, health beneficiary numbers		
Vehicle identifiers and serial numbers, including license plate numbers		
Check 'None' when none of the identifiers listed above will be recorded, maintained, or shared during the conduct of this study. (exempt category 4)	 None	 None

Data Analysis

Power analyses and study endpoints are not required for minimal risk research, pilot or feasibility studies.

No statistical information. *If checked, please explain:*

Power Statement: N/A

Data Analysis Plan

The pre-intervention and post-intervention, paper surveys' will be returned to the researcher for data entry and storage. The collected data will be collated and entered by the researcher into SPSS for data analysis. A detailed code book has been developed to include specific information on the type of variable and the theoretical and operational definitions. Data entry will be double-checked for accuracy by one of the staff trained staff RNs participating in data collection and chart audits. Descriptive statistics will be performed on each study variable. Continuous variables, including pain scores, pain knowledge, and opioid requirements, will be reported using a mean and standard deviation. Categorical variables, including patient characteristics and education engagement, will be reported as frequencies and percent occurrence. The data will be examined for any baseline differences between the groups to identify characteristics that may confound results and require control in the analysis. Data will be examined to assure that it meets the assumptions of normality required for parametric analysis. If data does not meet normality assumptions, nonparametric analyses will be used. This study uses a revised adaption of the Patient Pain Questionnaire (PPQ) survey. For this reason, the reliability and validity of the nine knowledge based questions will be evaluated using Cronbach's alpha and factor analysis.

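### The protocol gives two schedules for the APS-POQ-R; one leaves no pre-operative pain rating described, and the other asks patients before surgery about hospital care they have not yet had

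*Combined protocol and SAP*

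**What the plan says.** The last paragraph of Pain knowledge, under Instruments, sets two time points for both questionnaires: "At the start of the study and at the time of discharge the patient will complete the APS-POQ-R and the revised knowledge-based PPQ surveys". Later in that paragraph only one hand-out is described: "These paper and pencil surveys will be provided to the patient prior to discharge and collected from the patient".

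The start of the study can be dated from two other places. Recruitment and Consent says "At the start of the study the patient will be asked to complete the HIPAA Authorization", and the Design section has that form given at the pre-operative visit, of which it says "This typically occurs one to two days before surgery".

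The Data Collection Procedure describes the same visit differently. After the HIPAA form, "demographic and past medical history information and pain knowledge survey will be administered in the ambulatory clinic". The APS-POQ-R then appears only at the end of the stay: "At the time of discharge the patient will complete the Revised American Pain Society Patient Outcomes Questionnaire".

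On analysis, the Data Analysis Plan says "The data will be examined for any baseline differences between the groups to identify characteristics that may confound results" and may need controlling for. The test it names for comparing the groups is an independent t-test with no covariate. Limitations mentions a paired pre/post test, for pain knowledge.

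**The concern.** The two sections give different assessment schedules for the instrument that carries the pain and participation outcomes, and each has a problem.

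- **Under the Data Collection Procedure**, the supplied text describes no pain rating before surgery. The intake form (Patient demographics and clinical characteristics) takes chronic pain history, pre-operative opioid use and anxiety about anticipated pain. The chart audit adds no pain score.
- **Under Instruments**, the whole form is completed one to two days before surgery. Its items on side effects of treatment, helpfulness of information and participation in treatment decisions would then refer to inpatient care that has not happened.

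This matters because of how the arms are formed. The design is declared quasi-experimental, the arm follows the care unit, and units are filled according to bed availability. Bed control is asked only to split patients evenly. The text calls this random but describes no randomisation of individual patients, so balance on pre-operative pain is not assured. A rating not taken before surgery cannot properly be recovered afterwards.

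**Working it through.** **1. The schedules side by side**

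| Time point | Instruments (Pain knowledge) | Data Collection Procedure |
|---|---|---|
| Pre-operative visit | APS-POQ-R and PPQ | Demographics, history, PPQ |
| Discharge | APS-POQ-R and PPQ | APS-POQ-R and PPQ |

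The PPQ baseline is secure under both. Only the APS-POQ-R baseline is in doubt.

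**2. The plan's own sample size.** Inputs from Sample Size: d = 0.50, power 80%, alpha 0.05. Sidedness is not stated. A two-sided two-sample t-test needs 63.77, so 64 per arm, with power 80.1% at 64. The one-sided version needs about 51 and does not match. The stated 64 reproduces and does not depend on any baseline score.

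**3. What a baseline covariate could add.** Let r be the within-arm correlation between an item before surgery and the same item at discharge. The documents do not give r, so 0.1 to 0.6 is an assumption. Adjustment multiplies the residual variance by 1 − r², so the effective d is 0.50/√(1 − r²). For example, at r = 0.3 it is 0.50/√0.91 = 0.524.

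| r | 1 − r² | effective d | power at 64 per arm | n per arm for 80% (rounded up) |
|---|---|---|---|---|
| 0 (unadjusted) | 1.00 | 0.500 | 80.1% | 63.8 (64) |
| 0.1 | 0.99 | 0.503 | 80.5% | 63.1 (64) |
| 0.2 | 0.96 | 0.510 | 81.7% | 61.3 (62) |
| 0.3 | 0.91 | 0.524 | 83.7% | 58.1 (59) |
| 0.5 | 0.75 | 0.577 | 90.0% | 48.1 (49) |
| 0.6 | 0.64 | 0.625 | 93.9% | 41.2 (42) |

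The one degree of freedom spent on the covariate is ignored.

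**4. Bias from a systematic difference between units.** If the units differ in mean pre-operative pain by δ SD, and the SD is the same at both times, the unadjusted comparison is biased by r × δ. Take δ = 0.2, an assumption:

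- r = 0.1: 0.1 × 0.2 = 0.02 SD, which is 0.02/0.50 = 4% of the design effect.
- r = 0.3: 0.06 SD, or 12%.
- r = 0.6: 0.12 SD, or 24%.

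**5. Chance imbalance is a separate matter.** At 64 per arm the standard error of a baseline difference is √(2/64) = 0.177 SD. A difference of 0.2 SD is 0.2/0.177 = 1.13 standard errors (two-sided p about 0.26). As a chance event, that is sampling variation which the t-test's error rate already covers. The figures in step 4 apply only to a systematic difference.

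**The case against.** The strongest reply is that the start-of-study wording is a drafting slip. The same paragraph describes a hand-out only before discharge, Limitations speaks of pre-testing knowledge only, and the Data Collection Procedure agrees with both. The Procedure also leaves the APS-POQ-R off the pre-operative list without forbidding it, and it refers to Appendix G for the data collection protocol, which may settle the matter. This is a fair account of what was probably meant. It does not remove the conflict, because the two sections would still disagree, and the discharge-only reading is the one with no described baseline.

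A reader might also infer more than the text supports:

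- **That a planned adjustment is lost.** No section specifies a baseline-adjusted analysis of pain; the named test is unadjusted. What suffers is the conditional promise to examine and control baseline differences.
- **That pain-related confounding could not be examined at all.** Chronic pain history, pre-operative opioid use, anxiety, mental health conditions and past major orthopaedic surgery are collected, and the chart audit confirms the history of chronic pain, opioid use and mental health conditions. These are usable proxies, though none is the same-item score.
- **That no baseline pain score exists.** Appendix D and the code book are not supplied, so the most that can be said is that none is described.
- **That precision would certainly improve much.** Pain before joint replacement may be only weakly related to pain at discharge. At r of 0.1 to 0.2 the gain is negligible.
- **That the comparison is known to be biased.** The documents give no evidence of a systematic difference between units. They describe some protection: the intervention unit is chosen at random, bed control gets no direction on unit, and the researcher is blinded until bed assignment.

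**Conclusion.** The point holds as an unresolved conflict over when the APS-POQ-R is given, with a consequence for the data collected. On the discharge-only schedule, the baseline check for pain would rest on proxies, in a design where arms follow care units. On the two-time-point schedule, some items cannot be answered sensibly before surgery. The sample size of 64 per arm, the knowledge baseline and the paired knowledge test are not affected.

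The size depends on an r that the documents do not give. Over an assumed 0.1 to 0.6, power at 64 per arm and d = 0.50 goes from 80.1% unadjusted to between about 80.5% and 94%, so the gain may be negligible or substantial. An assumed systematic 0.2 SD difference between units would leave an unadjusted bias of about 0.02 to 0.12 SD. The change is worth making even so: it is cheap before enrolment and impossible to make good afterwards.

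**What to change.** 1. Make Instruments, the Data Collection Procedure and Appendix G state one schedule.
2. At the pre-operative visit, with the PPQ, give the APS-POQ-R items that can be answered then: pain severity, interference with activity and sleep, and emotions. Give the full form at discharge.
3. In the Data Analysis Plan, compare discharge pain scores by a linear model (ANCOVA) with arm and the same item at baseline, in place of the unadjusted t-test.
4. State that participation has no baseline.

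**Cost.** A wording amendment, and a few more items on paper forms already handed out at that visit, with a small added burden for each patient. Selected items would be used before surgery rather than the full questionnaire, so the reliability figures quoted under Pain outcomes (Cronbach's alpha 0.86 overall) do not carry over directly to the pre-operative set. No change to the sample size is needed.

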- Determine if there is a significant difference in opioid requirements in the first 48 hours according to the type of education delivery methods.

Background (Include relevant experience, gaps in current knowledge, preliminary data, etc.):

Despite all the available analgesic, modern devices, and nonpharmacological interventions, pain in the acute post-surgical period remains a prominent issue and effective management has remained elusive with significant gaps in care. Early estimates suggest that anywhere from 50% to 75% of surgical patients experience inadequate pain relief (Huang et al., 2001), often due to delayed intervention (Sinatra, Torres, & Bustos, 2002). A National Survey of patients who had undergone non-specific surgical care demonstrated occurrence of acute pain in 80% of patients and moderate to severe pain in approximately 86% of those who experienced acute pain (Apfelbaum, Chen, Mehta, & Gan, 2003). A 2008 study of 1,490 surgical inpatients, 41% of patients reported severe pain in the first 24 hours after surgery (Sommer, de Rijke, van Kellef, et al., 2008). Watt-Watson, Stevens, Garfunkel, Steiner, & Gallop (2001) found severe pain in 86% of coronary artery bypass patient 24 hours after surgery. A chart review revealed that 80% of these patients experiencing severe pain received <16 mg of morphine over the previous 24 hours and two had no analgesia orders in the medical record (Watt-Watson et al., 2001). Ineffective pain management effects recovery, complications, cost (Gordon, Dahl, & Stevenson, 2000), patient satisfaction (Garinella & Cellini, 2013), length of stay (Joshi, Beck, Emerson, et al., 2014), readmissions (ASA, 2012), quality of life (Ersek, 2001), and chronic postsurgical pain (O'Brien, Pergolizzi, van de Laar, et al, 2103; Barrington, Halaszynski, & Sinatra, 2014).

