
Study Design and Methods

Methods: *Describe, in detail, the research activities that will be conducted under this protocol:*

Variables

The independent variable is the type of patient education deliverable given to the two study arms, group A (experimental group, real-time, interactive, mobile education system) and group B (control group, standard of care). The dependent variables are 1) patient knowledge, 2) patient perceived participation in pain management, 3) high and low pain scores, and 4) total opioid consumption. A simple table of the independent, dependent, and additional variables are presented in Appendix B. A detailed accounting of all data points including variable type, theoretical definitions, and operational definitions can be found in the detailed code book.

Method

Design

This prospective study has been designed as quasi-experimental study. This study design was selected for several reasons. This study seeks to explore both a treatment and control group in efforts to compare outcomes which are dependent on the type of intervention. To control for fidelity of the intervention and avoid cross over, behavior changes from nurses providing the intervention, the intervention the patient receives will be determined by the location they are bedded in hospital. Orthopedic TJA patients are assigned at random and based on bed availability to one of two patient care units. One of the two patient care units will offer standard education the other unit will offer the mobile, iPad based education. The patient care unit to offer the mobile, iPad based education will be selected at random. This study design will help minimize will reduce the risk of selection bias, increase fidelity of the intervention, and increases the probability that the differences demonstrated between the study groups will be attributed to the actual intervention under study.

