Chart audits. Chart audits of the electronic health record will be conducted after discharge to collect the remaining clinical data. Data to be collected will include total opioid requirements as indicated by the medication administration record; primary surgical procedure as reported in the surgical listing and the operative report; type of regional anesthesia as indicated in the anesthesia record; length of stay; and discharge disposition as reported in the hospital dismissal summary. Additionally, the past medical history will be reviewed to confirm patient reported history of chronic pain, preoperative use of opioids, and mental health conditions. The researcher and a staff RN will conduct these chart audits.

Limitations

The design of this study does present some limitations. Participants in the study group will receive enhanced pain content that is delivered using an alternative method, ultimately testing both the delivery method and the content. The duality of the study intervention is a confounding variable and may make differentiating

the cause of the outcome difficult. Another limitation is that preoperative educational classes are available to patients to attend if they choose. All patients receive the same pamphlets and information in the mail when surgery is scheduled. An in-person didactic class is optional for patients. Some pain education is offered in this class. Currently only 49% of patients attend these classes. It is anticipated that some patients enrolled in the study will have received varying levels of education prior to their hospital admission. This is an antecedent variable that will be collected as part of the chart audit and accounted in the data analysis. The two nursing units involved in the study are located within the same hospital. It is possible that nursing staff from the intervention unit may float to the control unit and educate study patients using content from the expanded education from the intervention on the iPads. Pre-testing knowledge of pain and measured again at the end of the intervention (prepost) using a paired t-test analysis will strengthen the design of the study. Only opioid use for pain control is being measured.

Data Management

Data Collection Procedure

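### The 48-hour opioid window appears only in the fourth aim; the outcome definition and chart-audit instructions ask for a total with no cut, so a figure abstracted as written would not match that aim

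*Combined protocol and SAP*

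**What the plan says.** The opioid outcome is described in five places in the protocol.

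- **Research Question and Aims**, fourth aim: whether there is a "significant difference in opioid requirements in the first 48 hours" between the education methods. The start of the 48 hours is not given.
- **Variables**: the fourth dependent variable is "4) total opioid consumption", with no window.
- **Instruments, Chart audits**: "Data to be collected will include total opioid requirements as indicated by the medication administration record", with no window.
- **Data Collection Procedure**: after discharge the researcher will "collect clinical data including opioid consumption totals, past medical history, anesthesia type, and length of stay", again with no window.
- **Data Analysis Plan**: "Continuous variables, including pain scores, pain knowledge, and opioid requirements, will be reported using a mean and standard deviation". The arms are then compared by an independent t-test. Neither a window nor a dose unit is named.

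Three other statements bear on the point. The Data Collection Procedure places the start of the education on the ward: "The intervention will occur on the postoperative inpatient care unit (PCU) starting at the time the patient arrives on the unit". It then continues to discharge. The Design section makes arm identical to nursing unit, since one unit delivers the iPad education and the other standard education. Finally, the Variables section and the Data Analysis Plan say that operational definitions are held in a detailed code book, and the Data Collection Procedure refers to Appendix G for the collection protocol. Neither is part of the text available for this review.

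**The concern.** A 48-hour amount and a whole-stay amount are different outcomes. Someone reading a closed chart after discharge, asked for the total, would naturally add up the whole stay. Every patient who stays past 48 hours and is still taking opioid would then contribute doses that the aim leaves out.

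The mismatch matters more here than in an individually randomised trial with mixed wards. A whole-stay total depends on how long the patient stays, and discharge practice can differ between nursing units. With one unit per arm, such a difference cannot be separated from the education. It could appear as an opioid effect, or hide one, when use in the first 48 hours is the same. Length of stay is collected, but the protocol does not link it to the opioid comparison.

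The Endpoints section lists primary and secondary endpoints as not applicable. Nothing else in the text therefore fixes which version of the outcome is to be reported.

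**Working it through.** **1. The passages side by side**

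| Place | Window | Clock start | Dose unit |
|---|---|---|---|
| Fourth aim | First 48 hours | Not stated | Not stated |
| Variables | None | Not stated | Not stated |
| Chart audits | None | Not stated | Not stated |
| Data Collection Procedure | None | Not stated | Not stated |
| Data Analysis Plan | None | Not stated | Not stated |

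The window appears once, in the aim, and in none of the four places that define, collect or analyse the outcome.

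**2. The plan's own figure**

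The Sample Size section gives 64 per arm for d = 0.50, 80% power and alpha 0.05. The two-sided two-sample t-test needs 63.8 per arm, so 64, and power at 64 is 80.1%. The figure reproduces. It is unit-free and not tied to the opioid outcome, so this point does not change it.

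**3. How length of stay could enter (illustration only)**

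The protocol gives no opioid mean, opioid SD or length of stay. The following are assumptions:

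- 48-hour use X has mean 1 (arbitrary scale) and coefficient of variation 0.6, so E[X²] = 1 + 0.36 = 1.36.
- Daily use after 48 hours is half the earlier daily rate. The earlier rate is X/2 per day, so the later rate is 0.25X per day.
- All stays exceed 48 hours, with mean 3 days and SD 1 day. The excess stay E therefore has mean 1 and SD 1, independent of X.
- The other unit has the same 48-hour use and the same SD of stay, but a mean stay longer by 0.5 or 1 day.

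Whole-stay total: T = X(1 + 0.25E).

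Mean of T = 1 + 0.25·mean(E) = a.

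Variance of T = 1.36·(a² + 0.25²·1²) − a².

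| Unit | a | Variance of T |
|---|---|---|
| Reference | 1.25 | 1.36 × 1.6250 − 1.5625 = 0.6475 |
| 0.5 day longer | 1.375 | 1.36 × 1.9531 − 1.8906 = 0.7656 |
| 1 day longer | 1.50 | 1.36 × 2.3125 − 2.2500 = 0.8950 |

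Spurious standardised difference, using the average of the two variances:

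- 0.5 day: (1.375 − 1.25)/√0.7066 = 0.125/0.841 = 0.15
- 1 day: (1.50 − 1.25)/√0.7713 = 0.25/0.878 = 0.28

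The true 48-hour difference is zero in both cases. At 64 per arm, the t-test power function at these values puts the chance of a two-sided p < 0.05 at about 13% and 36%, against the nominal 5%. With equal stays the spurious difference is zero.

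**4. What happens to a real effect when stays are equal (same assumptions)**

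Take a 30% reduction in opioid use.

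- 48-hour total: 0.30/√[(0.36 + 0.49 × 0.36)/2] = 0.30/0.518 = 0.58
- Whole-stay total, if the reduction persists to discharge: 0.30 × 1.25/√[(0.6475 + 0.49 × 0.6475)/2] = 0.375/0.695 = 0.54

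If the effect persists, the loss is small. If doses outside the window instead carry no effect and add uncorrelated variance of r times the in-window variance, d = 0.50/√(1 + r). That gives 0.45, 0.41 and 0.35 for r = 0.25, 0.5 and 1, with power at 64 per arm of 71%, 63% and 51%.

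**The case against.** The strongest reply is that the protocol assigns operational definitions to a code book it says already exists, and the collection protocol to Appendix G. Either may state the 48-hour limit. A total is also not the opposite of a 48-hour amount: it can mean the sum of all doses within the aim's window, and nothing prevents that sum from being taken from the medication administration record. The abstractors are the researcher and a nurse trained by the researcher. This stands, and it limits the point to the text as written.

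It does not remove the point. The outcome definition and both abstraction instructions omit the limit that the aim sets, and a code book that supplied it would still leave those passages to be aligned.

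A reader might infer three stronger things that the documents do not support.

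- **That the trial will certainly collect a figure unable to answer the fourth aim.** This holds only if the charts are abstracted as written.
- **That milligrams of unlike opioids will be added together.** The Data Analysis Plan gives the summary statistic and is silent on the unit. Silence is not a plan to add raw milligrams, so any power loss calculated on that basis describes a procedure the protocol does not contain.
- **That doses charted before arrival on the unit bias the comparison.** They precede the education, so with balanced allocation they add noise rather than bias, and the protocol does not say how large they are.

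It is also fair to say that a persisting effect would leave a whole-stay total nearly as sensitive as the 48-hour one. It would still answer a different question from the aim.

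**Conclusion.** The point holds in this form: the protocol sets a 48-hour opioid outcome in its fourth aim, and elsewhere defines and collects an opioid total without that limit. If abstracted as written, the figure is a whole-stay total that does not match the aim, and any difference in length of stay between the two units enters the comparison of arms.

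The size cannot be computed from the documents. The spurious differences of 0.15 and 0.28 rest on an assumed opioid distribution, an assumed later rate of use, stays all beyond 48 hours, and a hypothetical difference of 0.5 or 1 day between units. They show that the route is not negligible and do not estimate what will happen. The sample size is unaffected.

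The missing clock start is part of the same gap. The missing dose unit is a matter for clarification only, because the code book may supply it.

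**What to change.** Use one definition in the fourth aim, Variables, Chart audits, Data Collection Procedure and Data Analysis Plan: the opioid total over 48 hours from a stated clock start. Arrival on the inpatient unit, when the education begins, is the natural start, for the sponsor to confirm. Have abstractors record the time of each dose so that the cut can be applied. State also what is recorded for a patient discharged before 48 hours. If the code book or Appendix G already sets the window, align the protocol text with it.

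Report any whole-stay total only as a separate descriptive variable. As a clarification, confirm that the code book names one opioid-equivalent unit and its conversion table.

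The cost is wording in the protocol and code book, one change to the abstraction form, and slightly longer abstraction per chart from a record already being audited. No extra patients are needed and treatment is unchanged. The change removes the length-of-stay route for patients who stay at least 48 hours. It does not remove other differences between the two units.
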